## Research Protocol/Protocol Addendum Template

---

**BESST Intervention Description:** Patients assigned to the BESST intervention will receive the BESST Intervention plus the standard care. The BESST intervention is an adaptation of the VA BIC intervention and designed to meet the unique needs of Veterans receiving care in a VA-CCN mental health treatment setting (**see BESST Manual**). BESST can be delivered by a trained mental health staff member, such as a mental health nurse, social worker, psychologist, or psychiatrist. The intervention targets the needs of patients who are being discharged from a higher-level care setting (e.g., acute inpatient, residential). The intervention incorporates aspects of motivational interviewing (MI) techniques. Because the intervention is intended to complement and enhance standard care, patients assigned to the BESST intervention will continue to have access to care (described below). There are no restrictions on the types of treatments that patients may pursue after discharge from the VA-CCN mental health treatment setting.

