**Regular Contact:** The patients will maintain regular contact with the intervention staff member for a total of seven contacts over the course of the three months after discharge. At each of these contacts, the intervention staff member will monitor the patient's symptoms, assess treatment adherence, review the safety plan with the patient, and, if necessary, assist the patient with engaging in care. The contacts are designed to be highly interactive, allowing time for questions and providing patients with written materials that they can keep for future reference. Depending on the patient's preference, the regular contacts will be delivered over the phone (or VA Video Connect) or in-person in a private office on the grounds of the WRJ VAMC. These visits last roughly 15-30 minutes.

**Standard Care:** Regardless of study assignment, all patients will have access to standard care. This includes recommendations for mental health follow-up as deemed appropriate by the discharging treatment team. Patients may also be offered specific treatments to address their mental health symptoms after discharge. It is also conceivable that a patient may be on the High Risk for Suicide List. Patients on the High Risk for Suicide List receive enhanced oversight as

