## Research Protocol/Protocol Addendum Template

---

assessments. The BSS is a self-reported questionnaire that assesses severity of suicidal ideation. The BSS measures attitudes, behaviors, and plans to die by suicide. Each item on the BSS is scored on a scale from 0 to 2 and the first 19 of the 21 items are used to calculate a total score ranging from 0 – 38. The BSS has high reliability and is a valid measure of suicidal ideation. The BSS may be a measure of risk of suicide. There is evidence that the BSS is measurement invariant across time.

**Secondary Outcome (Patient Engagement):** We will measure patient engagement in treatment at baseline and at follow-up assessments in two ways. First, we will examine healthcare utilization in the first three months after discharge. We will look at the amount of contact with mental health providers as well as the time to first mental health appointment after discharge. We will also evaluate evidence of disruptions of care such as no-show and cancelled appointments. We will abstract these measures from the electronic medical record. Since it is possible that some patients may receive portions of their care outside of the VA system, we will also ask patients to self-report on non-VA care. To gather data regarding the patient's sense of self-efficacy around managing their suicide risk after discharge, we will administer the validated Suicide-Related Coping Scale (SRCS). This SRCS includes 17 questions related to a patient's perception of their ability to cope with suicidal thoughts. Each item is assessed using a 5-point Likert scale and the measure has been developed based on two studies of suicide prevention strategies conducted within Veteran populations. The scale includes two subscales including an External Coping subscale and an Internal Coping Subscale. Both subscales have shown good acceptable internal consistency. The two factors are also sensitive to change over time. Higher scores on the scale suggest better coping. In addition to the SRCS, we will also measure the patient's general sense of self-efficacy using the General Self-Efficacy Scale (GSE). This is a valid scale of self-efficacy that is designed for the general population (12 years or older) and it has been tested in various countries.

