### ***Therapeutic Risks***

During the study, the research staff will ask patients questions about how they are feeling and their interactions with other people. Patients will be exposed to these therapeutic risks during the baseline and each follow-up assessment. In addition, patients who receive the intervention condition will also be exposed to these therapeutic risks at the intervention visits (brief education visit plus seven contact visits after discharge). In some cases, patients can feel embarrassed, nervous, bored, or generally uncomfortable when they are asked to answer these types of questions. However, because we have sufficient safeguards in place to mitigate these potential risks, we believe that the overall therapeutic risk from this study to enrolled patients is very low.

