### ***Protection Against Risk***

#### *Study Population Safety Risk*

At each study assessment time point (i.e., baseline and one-month, and three-month follow-up), patients will be assessed for symptoms of suicidal ideation and suicidal behavior because these are *a priori* study endpoints. In addition, for patients receiving the intervention, patients may report worsening suicidal ideation or suicidal behavior in the context of the intervention visits. Regardless of whether the patient is receiving the intervention or is assigned to usual care alone, the study staff will be ethically bound to take appropriate action if the patient is at imminent risk for self-harm. The Safety Alert Protocol outlines the process that study staff members will take in order to ensure the safety and well-being of all enrolled patients regardless of whether they are receiving the intervention or usual care alone. In the case that a safety alert is met, the research staff member will contact [name] (or the mental health physician covering for her) or, if necessary, the patient's mental health provider. As part of this risk assessment, the assessing clinician will immediately complete a comprehensive evaluation of

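### Engagement outcome: no rule separates BESST's own sessions from mental health care, and time to first appointment has no analysis suited to patients who are never seen

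*Combined protocol and SAP*

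**What the plan says.** Under Secondary Outcome (Patient Engagement), the utilization measures are contact and timing ("We will look at the amount of contact with mental health providers as well as the time to first mental health appointment after discharge") and disruption ("We will also evaluate evidence of disruptions of care such as no-show and cancelled appointments"). All are abstracted from the electronic record for the three months from discharge, and patients also self-report care outside the VA.

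On who delivers the intervention, BESST Intervention Description says: "BESST can be delivered by a trained mental health staff member, such as a mental health nurse, social worker, psychologist, or psychiatrist". On quantity, Therapeutic Risks gives "brief education visit plus seven contact visits after discharge". Regular Contact places the seven contacts in the outcome window: "for a total of seven contacts over the course of the three months after discharge". Brief Educational Intervention expects the first session about one to two weeks after entry.

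For the trial's secondary outcomes, Statistical Analyses, Specific Aim 2 names two methods. One is a mixed model with arm and linear time, for continuous variables, with missing data handled by maximum likelihood. The other is chi-squared, for a categorical utilization measure whose categories are not defined.

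**The concern.** There are two gaps.

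The first is a missing counting rule. A session given by a psychologist or social worker in the window can fit the literal definition of the outcome, and only one arm is offered such sessions. An abstractor has no written instruction to leave them out. If they went in, the outcome would partly record that BESST was delivered. A reader could not tell that from the re-engagement in VA care that Specific Aims/Purpose sets out to measure. The direction is not the same for every measure: sessions held would help BESST on contacts and timing, and sessions missed would hurt it on no-shows.

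The second is the analysis of time to first appointment. It is not a repeated score, so a model of change over time does not describe it. A patient never seen has no value. With only one value per patient, maximum likelihood has no other measurement of that outcome to draw on, so that patient would in effect drop out. Those patients are the least engaged.

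**Working it through.** **Inputs from the plan.** Up to 25 patients; 1 + 7 = 8 BESST sessions; first session one to two weeks after entry; a three-month window, taken as 90 days; P < 0.05. The sample-size paragraph argues from the BSS only, so there is no engagement figure to reproduce.

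**Assumptions (not in the plan).** 13 BESST v 12 usual care; two-sided tests, counting one direction (nominal 2.5%). Visit and no-show counts are negative binomial with dispersion k. Time to first visit is exponential with rate −ln(1 − p)/90, where p is the proportion seen by day 90. The first session falls 7–14 days after entry, and 20% of patients enter 14–28 days late. Session completion is 75% unless stated.

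**Step 1: contact counts if sessions are counted, no true effect.** The mean shift is 8 × 0.75 = 6 contacts. The plan names no test for counts, so a t-test stands in. Ranges are over k = 1 to 3.

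| Sessions counted | Usual-care mean 4 | Mean 8 | Mean 12 |
|---|---|---|---|
| 8, 75% completed | 88–99% | 44–76% | 25–48% |
| 8, 50% completed | 60–85% | 23–43% | 14–25% |
| 2, 75% completed | 14–22% | 7–9% | 5–7% |
| 0 | 2–3% | 2–3% | 2–3% |

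Entries are the chance of a false significant result favouring BESST.

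**Step 2: first appointment if the first session is counted, no true effect.** The apparent proportion seen by day 90 in the BESST arm is 1 − (1 − p) × 0.25. For p = 0.5, 0.7 and 0.9 this is 0.875, 0.925 and 0.975. False results favouring BESST:

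| True attendance | Chi-squared, any visit by day 90 | Log-rank |
|---|---|---|
| 50% | 57% | 78% |
| 70% | 30% | 64% |
| 90% | 2% | 45% |

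These are uncorrected chi-squared values. With sessions left out, log-rank gives about 3%. An earlier cut-off is worse for chi-squared. With every BESST patient completing the first session, and 60–90% truly seen by day 90, a category of seen by day 30 gives 78–100%.

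**Step 3: no-shows.** If every uncompleted session is charted as a no-show, BESST gains 8 × 0.25 = 2 on average. False results against BESST are then 74–89%, 40–61% and 23–41% at usual-care means of 1, 2 and 3 (k = 0.5 to 2). If only 10% of sessions are charted that way (8 × 0.10 = 0.8), the rates at k = 1 are 26%, 13% and 9%, against 83%, 50% and 31%.

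**Step 4: choice of test, BESST sessions excluded, true effect present.** At 90% v 50% attendance, the expected number with no time is 13 × 0.10 = 1.3 in BESST and 12 × 0.50 = 6 in usual care. Power:

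| Attendance, BESST v usual care | Log-rank | Chi-squared, any visit | t-test, attenders only |
|---|---|---|---|
| 90% v 50% | 70% | 65% | 14% |
| 80% v 40% | 59% | 56% | 9% |
| 95% v 70% | 54% | 37% | 18% |

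Log-rank gains most over chi-squared when nearly everyone is eventually seen and the arms differ mainly in speed.

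**Step 5: the clock at discharge.** At 90% v 50%, log-rank power falls from 70% to 65% if 20% enter late, and to 60% if 40% do. With no true effect and 40% late, the false-positive rate is 2.6%.

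**The case against.** A reader might infer that the trial will count its own sessions and that its engagement result will therefore be biased. The documents do not support that. No passage says that sessions are charted in the medical record or counted. The text leans the other way. BESST is given by intervention staff, and Resources Available lists the interventionist as research staff. Its relation to care is stated as "Because the intervention is intended to complement and enhance standard care", and one task is to "assist the patient with engaging in care". Study Population Safety Risk has research staff contact the study's own physician or "if necessary, the patient's mental health provider", so the two roles are distinct. Protected Health Information puts study data in a separate capture system. The BESST Manual and Figure 3 are not available here, and the pages on Aims 1 and 2 were left out on purpose, so a rule may exist elsewhere. This stands: the bias is conditional, and the gap is an unwritten rule.

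A reader might also infer that neither named test can accommodate patients never seen. That goes too far. Chi-squared on a yes/no visit places them in the no category and loses nobody. Its limits are that no category or cut-off is defined and that a proportion is not a time. Nor does any passage propose analysing attenders only; that column shows what follows if the time is treated as an ordinary continuous variable.

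The largest rates in Steps 1 and 2 come from a t-test and a log-rank test, which the plan does not tie to utilization. For chi-squared on any visit by day 90, the conditional bias runs from 57% down to 2%.

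Finally, late entry might be read as a source of bias. It dilutes an effect slightly and favours neither arm.

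**Conclusion.** The point holds in a limited form, for a secondary outcome. The supplied text does not exclude BESST sessions from the engagement measures. If they were charted and counted, contacts and timing would favour BESST and missed sessions charted as no-shows would count against it. The size ranges from slight, with two sessions counted against a high background of visits, to near-certain false significance, with all eight counted against a low one. Whether this would happen cannot be settled from the documents.

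The analysis gap does not depend on that condition. The mixed model does not fit time to first appointment, and chi-squared gives up the timing. Log-rank has the highest power of the three approaches in every scenario examined; its margin over chi-squared is 3 to 17 percentage points (59 − 56 and 54 − 37). All attendance, visit and completion rates are assumed, so these figures show direction and rough size and do not predict the trial's results. The primary BSS analysis is not touched.

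**What to change.** Amend Secondary Outcome (Patient Engagement) and Statistical Analyses, Specific Aim 2 before abstraction begins:

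- **Counting rule.** Count only non-study mental health visits, no-shows and cancellations, by the same rule in both arms. Report BESST sessions held and missed separately, as intervention exposure.
- **Time to first visit.** Analyse time to first non-study mental health visit by Kaplan-Meier and log-rank, with patients never seen censored at the end of the three-month window.
- **Counts and binary measures.** Compare visit, no-show and cancellation counts with a rank test or a count model. Keep chi-squared for binary measures such as any visit.

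The clock can stay at discharge, with the small dilution in Step 5 accepted.

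The cost is a few sentences in the plan and a study-encounter flag at abstraction. No patient visits are added. The engagement effect may look smaller than if study sessions had been included.

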## Research Protocol/Protocol Addendum Template

behaviors. The scale asks the assessor to document the actual and potential lethality of these behaviors. The C-SSRS is widely used in the VA.

**Secondary Outcome (Substance use):** We will assess substance use at baseline and follow-up assessments using a timeline follow-back approach. This method is commonly used in research studies to assess substance use patterns.

**Study Design:** As shown in **Figure 3** below, patients allocated to the BESST intervention will meet with the intervention staff around the time of discharge. During this visit, the patients will receive a brief educational intervention. Depending on patient preference, this visit will occur over the phone (or VA Video Connect). Depending on patient preference, the regular contacts will occur in a private office on the WRJ VAMC campus, or the contacts will occur over the phone (or VA Video Connect).

**Figure 3.** Schedule of Assessments and Interventions.

BIC= VA Brief Intervention and Contact Program; D/C = discharge; dy = days; m = months; MH = Mental Health; T0, T1, T2 = assessment time points; wk = weeks

All patients (including patients randomized to the intervention) will have access to standard care. Furthermore, regardless of study assignment, all patients will undergo outcome assessment at baseline (0M), one month (1M), and three months (3M). These assessments will be conducted by the independent outcome assessor. We anticipate that, in most cases, the baseline assessment will occur around the time of discharge. However, because patients will be recruited remotely, we anticipate that the baseline assessments may in some cases happen a few weeks after discharge. Depending on patient preference, the independent outcome assessor will conduct the follow-up assessments in a private office on the WRJ VAMC campus, over the phone, or using VA Video Connect. The assessors will be blinded to study assignment and the patients will be instructed to not reveal their status to the assessor.

Because we are recruiting patients from a large geographic area (New Hampshire, Maine and Vermont), we anticipate that several enrolled patients will prefer phone (or VA Video Connect) over in-person follow-up. Fortunately, the assessment instruments that we selected for this study can be administered over the phone or in person.

**Statistical Analyses:** We will conduct the analysis based on the intention-to-treat principle. Below, we have outlined the specific analysis plan for assessing each of the primary and

## Research Protocol/Protocol Addendum Template

---

secondary aims of interest of this study. We will assess for statistically significant differences in baseline study characteristics such as age, sex, race, and mental health diagnosis, between study arms using *t*-tests for continuous measures and chi-squared tests for dichotomous variables. We will report these results using 95% confidence intervals (CI) and *P*-values. We will define statistical significance as a *P*-value < 0.05.

**Specific Aim 1:** We will generate descriptive summary statistics (e.g., means and standard errors, medians) and graphical displays for the BSS total scores at baseline and at each of the follow-up assessments. In the case of the pilot study of the BESST intervention in up to six patients, we will use a repeated measures analysis of variance (ANOVA) test to assess for changes in continuous variables in the first three months after discharge. Second, if the repeated measures ANOVA suggested a significant difference in means across time, we will perform a post-hoc, pair-wise comparison of means at baseline and at each follow-up using a two-sample *t*-test.

With regards to the RCT of the BESST intervention, we will use a generalized linear mixed model to assess for changes in continuous variables in the first three months after discharge. We will consider allocation of study arm (categorical measure) and time (continuous measure) as fixed effects. Random effect will be used to account for correlation that arises from repeated measures of the same individual. We will assume a linear effect and model changes in suicidal ideation over time. We will calculate 95% CI and *P*-values and will define a *P*-value of < 0.05 to be statistically significant. We will use the maximum likelihood ratio to account for any missing data. Based on available evidence, we hypothesize that the BESST intervention plus standard care will lead to a significant reduction in suicidal ideation after discharge.

**Specific Aim 2:** We will generate descriptive summary statistics (e.g., means and standard errors, medians) and graphical displays for our secondary outcomes of interest at baseline and at each of the follow-up assessments. In the case of the pilot study of the BESST intervention in up to six patients, we will use a repeated measures analysis of variance (ANOVA) test to assess for changes in continuous variables in the first three months after discharge. Second, if the repeated measures ANOVA suggested a significant difference in means across time, we will perform a post-hoc, pair-wise comparison of means at baseline and at each follow-up using a two-sample *t*-test.

With regards to the RCT of the BESST intervention, we will use a generalized linear mixed model to assess for changes in continuous variables in the first three months after discharge. We will calculate the associated 95% confidence intervals and *P*-values. As with the BSS, we will consider allocation of study arm (categorical measure) and time (continuous measure) as fixed effects. Random effect will be used to account for correlation that arises from repeated measures of the same individual. We will assume a linear effect and model changes in suicidal ideation over time. We will define a *P*-value of < 0.05 to be statistically significant. We will use the maximum likelihood ratio to account for any missing data. Based on available evidence, we hypothesize that the BESST intervention plus standard care will lead to a significant reduction in our secondary outcomes after discharge.

For the categorical measure of healthcare utilization, we will use chi-squared tests to compare findings between study arms.

**Specific Aim 3:** We will not be powered to detect a statistically significant difference between study arms with regards to suicide deaths and suicide attempts. These events are very difficult to examine in a clinical trial. A study would need to recruit well over 1,000 patients. Because we assume that few events will be observed in either arm, we plan to summarize our results by

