## Research Protocol/Protocol Addendum Template

---

needs and concerns to their outpatient providers. Yet, the WHO BIC has not been studied in high-income countries or in U.S. veterans. Our pilot work demonstrated that the WHO BIC may address systematic vulnerabilities in the discharge process and align with hospitalized veterans' preferences for treatment.

We conducted a pre-post study of an adapted version of WHO BIC (called VA *BIC*) in nine psychiatrically hospitalized Veterans at the White River Junction VA Medical Center (WRJ VAMC). We found that rural Veterans exposed to VA BIC experienced significant and clinically meaningful improvements in suicidal ideation at one and three months after discharge. We also observed significant improvements in related measures of suicide risk including hopelessness and connectedness. Patients had high treatment engagement after discharge. Subsequently, we performed a pilot RCT of VA BIC in 19 psychiatrically hospitalized Veterans. Aligned with the results of our pre-post study, we found that VA BIC had a medium or large effect on suicidal ideation, hopelessness, social connectedness at one month after discharge. Furthermore, the effect on social connectedness remained large at three months. VA BIC also had a medium effect on treatment engagement.

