### **Project Proposal, Phase 3, Aim 3**

To test our hypotheses as described above, we propose to conduct an assessor - blinded RCT comparing the BESST intervention plus standard care to standard care alone. We will enroll up to 25 patients who are 18 years or older and are being discharged from a VA-CCN mental health treatment setting. The primary aim is to determine whether the BESST intervention reduces suicidal ideation at one and three months after discharge. The secondary aim is to evaluate the impact of the BESST intervention on other related measures of suicide risk including hopelessness, social connectedness, fatal/non-fatal suicide attempts and treatment engagement.

**Randomization:** Prior to the start of study enrollment, the study team otherwise not involved in recruitment will independently prepare allocation cards using a permuted block schedule. The same study staff member will then put these prepared allocation cards into sealed, opaque, numbered envelopes. After obtaining consent and completing the baseline assessment (see description below), the study staff member will take the next numbered envelope from the box (described above) and open the envelope to determine the patient's assignment. In the event that the patient has been assigned to the intervention, the study staff will notify the intervention staff in order that the intervention staff can initiate the intervention. Otherwise, the patient will be informed that they have been assigned to usual care.

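### The RCT model has only arm and linear time, so it gives one arm difference for all visits and cannot separate the one- and three-month effects in the primary aim; if the 0M score is modelled, it also dilutes the effect by about a third.

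*Combined protocol and SAP*

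**What the plan says.** **The aim.** Project Proposal, Phase 3, Aim 3 states: "The primary aim is to determine whether the BESST intervention reduces suicidal ideation at one and three months after discharge".

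**The model.** Statistical Analyses, Specific Aim 1 specifies a mixed model for the RCT. Its fixed-effects sentence reads "We will consider allocation of study arm (categorical measure) and time (continuous measure) as fixed effects", followed by a patient random effect of unstated form and "We will assume a linear effect and model changes in suicidal ideation over time". Specific Aim 2 uses the same structure for the continuous secondary outcomes: "we will consider allocation of study arm (categorical measure) and time (continuous measure) as fixed effects".

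**The visits.** Study Design counts the baseline visit among the outcome assessments ("all patients will undergo outcome assessment at baseline (0M), one month (1M), and three months (3M"). Under Randomization, the envelope is opened only "After obtaining consent and completing the baseline assessment".

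**What else is planned by visit.** For the RCT there are descriptive summaries and graphs at each assessment. The pairwise t-tests in the same section belong to the pilot of up to six patients.

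**The concern.** A model with arm and continuous time as its only fixed effects is two parallel straight lines. The gap between them is the same at every visit, so the primary analysis cannot say whether the intervention works at one month, at three months, or at both.

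What else is lost depends on details the plan leaves open:

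- **(a) The 0M score is a modelled outcome.** This is the natural reading, since the plan models change over the first three months and treats 0M as an outcome assessment. Because allocation follows baseline, the expected 0M arm difference is zero, and averaging that zero in pulls the estimate toward no effect.
- **(b) Only 1M and 3M are modelled.** There is no dilution. The result is the unadjusted two-visit average, which is usable but still cannot separate the visits.
- **(c) An arm-by-linear-time term was intended.** It is not written. It would tie the 1M effect to the 3M effect by a straight line that the documents do not establish. Preliminary Studies reports the team's earlier RCT by visit: "VA BIC had a medium or large effect on suicidal ideation, hopelessness, social connectedness at one month after discharge", and then only that "the effect on social connectedness remained large at three months". It gives no three-month ideation effect for that trial.

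The three readings give different estimates and different power, so leaving the choice open also allows it to be made after the data are seen.

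**Working it through.** **The plan's own figure.** Sample Size says that up to 25 patients give sufficient power. No SD, between-arm difference or numeric power is stated, so this cannot be reproduced.

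**Inputs from the documents.** Assessments at 0, 1 and 3 months; baseline before allocation; up to 25 patients; significance at P < 0.05.

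**Assumptions.** 13 versus 12 patients, two-sided test, normal scores with SD 1, identity link, random intercept, complete data. Within-patient correlation r = 0.5, with results for r = 0.3 and 0.7 in brackets. Variances below are multiplied by 1/13 + 1/12 = 0.1603; power is from the noncentral t.

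**Step 1: what the arm coefficient estimates.** Let e1 and e3 be the true effects at 1M and 3M.

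- (a) With 0M rows: (0 + e1 + e3)/3, which is two thirds of (e1 + e3)/2. Generalised least squares gives the same value at r = 0.3, 0.5 and 0.7.
- (b) Follow-up only: (e1 + e3)/2.

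For e1 = e3 = 0.8: (a) 1.6/3 = 0.533; (b) 0.800. For e1 = 0.8, e3 = 0.4: (a) 1.2/3 = 0.400; (b) 0.600.

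**Step 2: variances and degrees of freedom.**

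- (a) (1 + 2r)/3, df 23
- (b) (1 + r)/2, df 23
- (c) slope weights (−4/3, −1/3, 5/3)/4.667, variance (1 − r)/4.667, df 23
- Baseline-adjusted two-visit average: (1 + r)/2 − r², df 22
- Baseline-adjusted single visit: 1 − r², df 22

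Example for (a) at r = 0.5: variance (2/3) × 0.1603 = 0.1068, SE 0.327, noncentrality 0.533/0.327 = 1.63, power 35%.

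**Step 3: power.**

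| Analysis | 0.8 SD at both visits | 0.8 SD at 1M, 0.4 SD at 3M |
|---|---|---|
| (a) 0M in response | 35% (42, 30) | 22% (26, 19) |
| (b) 1M and 3M only | 60% (66, 55) | 38% (43, 34) |
| (c) arm × linear time | 39% (29, 58) | 10% (8, 13) |
| Adjusted average | 77% (72, 89) | 53% (48, 67) |
| Adjusted 1M | 60% (52, 76) | 60% (52, 76) |
| Adjusted 3M | 60% (52, 76) | 20% (17, 27) |

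In the first column, the step from 35% to 60% is the cost of reading (a). The further step from 60% to 77% is an efficiency gain from baseline adjustment, not an error in the plan.

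**Step 4: the straight line in (c).** With true effects 0, 0.80, 0.80 at 0, 1 and 3M, the fitted differences are 0.23, 0.46 and 0.91. With 0, 0.80, 0.40 they are 0.29, 0.37 and 0.54: a fading benefit is fitted as a growing one.

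**Step 5: simulation.** With 40,000 trials per setting (first column, r = 0.5), (a) gave 0.534 SD and 34.8% power; (b) gave 0.801 SD and 60.2%; (c) 38.5%; the adjusted average 75.2%. The adjusted analyses run one to two points below the formula. Rejection under no effect was 4.8% to 5.2% for every analysis, so type I error is not inflated.

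**Step 6: sensitivity of the one-third figure.** With a true effect of 5 points at both follow-ups, (a) expects 5 × 2/3 = 3.33. With 20% missing at each follow-up, 200 simulated fits averaged 2.89 (SE 0.12), a loss of about 42%. With a random slope (assumed slope variance 0.02 to 0.2; intercept and residual variance 0.5 each), the coefficient was 3.03 to 2.09, a loss of 39% to 58%.

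**The case against.** The best reply is that the aim does not say the two effects must be separated. The plan's own hypothesis is a single reduction after discharge, and a two-visit average is a legitimate primary contrast. On that view reading (b) loses only secondary estimates and precision. This is fair for (b), but the plan does not state (b), and it is not the natural reading of a model for change that counts 0M as an outcome assessment.

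Second, modelling change over time may be shorthand for an arm-by-time term. It may be, but the sentence lists two fixed effects, and a linear interaction would still not recover the two visit effects unless benefit grows in a straight line. Growing benefit is plausible, because the contacts run over three months, and in that case arm × linear time can beat the two-visit average (figures under the fix). That is a reason to choose the contrast in advance.

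Third, the one-third dilution is conditional: 0M in the response, random intercept, identity link, complete data. It is also relative to the mean follow-up effect; in the fading example the coefficient (0.40) equals the 3M effect and is half the 1M effect. These conditions stand. The departures tried, a random slope and missing follow-up, made the dilution larger.

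Fourth, if the descriptive means and standard errors are given by arm, a reader could compute a crude difference at each visit. The plan does not say they will be, and that would not be a prespecified comparison.

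Finally, this is a pilot, and visit estimates will be imprecise. True, but the plan tests at 0.05, hypothesises a significant reduction and claims sufficient power.

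**Conclusion.** The concern holds and should be fixed before analysis. That the model as written gives one arm difference for all visits follows from its two fixed effects and needs no numerical assumption. No other part of the plan supplies a prespecified comparison at one or three months.

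On reading (a), the estimate is also biased toward no effect: two thirds of the mean follow-up effect under the conditions given. In the illustration with equal effects at both visits, this costs about 25 points of power (60% to 35% at r = 0.5). On reading (b), the loss is the visit-specific estimates and the gain from baseline adjustment. On reading (c), the problem is the unsupported straight line. All power figures depend on an assumed effect size, correlation, allocation and complete follow-up.

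**What to change.** Replace the model sentences for the RCT in Specific Aims 1 and 2:

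- **Outcomes:** the 1M and 3M scores.
- **Fixed effects:** arm, visit (categorical), arm × visit, and the baseline score of the same measure.
- **Random effect:** patient.
- **Reporting:** the arm difference with 95% CI at 1M and at 3M.
- **Primary contrast:** one, named in advance, for example the two-visit average or the 3M difference.

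A longitudinal model that includes 0M but constrains the arms to a common baseline mean is an alternative.

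The change is to wording only and uses data already collected. Its costs are:

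- One or two degrees of freedom.
- If benefit truly grows linearly to 0.8 SD at 3M, the two-visit average has 40%, 44% and 57% power at r = 0.3, 0.5 and 0.7, against 38–39%, 50–51% and 71–73% for arm × linear time (the range reflects df 23 or 48). The adjusted 3M contrast has 52%, 60% and 76% there, but only 20% at r = 0.5 if benefit fades to 0.4 SD.
- Visit estimates are wide: 95% CI half-width about 0.72 SD per visit at r = 0.5 (0.79 at r = 0.3, 0.59 at r = 0.7), against 0.59 SD for the average (0.62, 0.50).
- Categorical visit does not use actual assessment timing, which matters because Study Design allows some baselines to fall weeks after discharge.
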